### 6.2.1 Phase 1 Single-Dose Safety Study

The safety, tolerability, and PK of a single subcutaneous dose of nemolizumab were evaluated in a randomized, double-blind, placebo-controlled phase 1 study including 80 healthy adult volunteers and 36 Japanese subjects with moderate-to-severe AD. Doses ranged from 0.003 to 3.0 mg/kg in healthy volunteers and from 0.3 to 3.0 mg/kg in AD subjects. There were no deaths or serious adverse events (SAEs)

CONFIDENTIAL

reported in the study, and no dose-dependent increase in the incidence of adverse events (AEs) was observed.

Pharmacokinetic assessments following a single subcutaneous dose of nemolizumab showed a dose-dependent increase in serum nemolizumab concentration,  $AUC_{inf}$ , and maximum drug concentration. Peak serum concentrations were observed 4 to 6 days after nemolizumab administration, after which the drug gradually disappeared over a half-life of approximately 2 weeks.

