## 9 STUDY ASSESSMENTS

A written, signed ICF, assent form, and Health Insurance Portability and Accountability Act (HIPAA) authorization is required before any study-related procedures are performed.

Upon provision of the signed ICF/assent form, each subject will be assigned a unique SIN. For the duration of the entire clinical study, the subject will be identified using the SIN in all documentations and discussion.

The planned study assessments are in Section 8.1.2 . At each visit, assessments/procedures should be performed in the following order:

1. Patient-reported efficacy and safety measurements
2. Investigator assessments (including efficacy and safety)
  - ECG should be done before vital signs measurements (and blood draws).  
See Section 9.2.10
3. Sample collections for laboratory assessments
4. Sample collections for correlative assessments (PK, ADA, PD, and optional PGx)
5. Administration of study drug injections

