### 9.1.3 Pruritus Numeric Rating Scale

The Pruritus NRS is a scale to be used by the subjects to report the intensity of their pruritus (itch) during the last 24 hours (see [Appendix 6](#)). Two measures of Pruritus NRS will be assessed (average and peak/maximum itch intensity). The PP NRS has been validated in other AD clinical trials in adults, and the minimum clinically important difference was shown to be 4.

CCI

Subjects will be asked the following questions:

[figure not shown]
CCI

- For maximum itch intensity (PP NRS): “On a scale of 0 to 10, with 0 being ‘no itch’ and 10 being the ‘worst itch imaginable’, how would you rate your itch at the worst moment during the previous 24 hours?”

[figure not shown]
The screening PP NRS will be determined by a single assessment using the PP NRS (score ranging from 0 to 10) for the 24-hour period immediately preceding the screening visit. The baseline PP NRS will be determined based on the average of daily PP NRS (score ranging from 0 to 10) during the 7 days immediately preceding baseline (rounding to nearest whole number is not permitted). A minimum of 4 daily scores out of the 7 days immediately preceding baseline is required for this calculation. Subjects will receive instructions on how to record their pruritus NRS scores and will complete the assessment once daily in the evening throughout the clinical study (including the run-in and the follow-up period).

CONFIDENTIAL

The proportion of “itch-free days” will be calculated from the number of subject-reported PP NRS and CCI scores of 0 or 1 during the treatment period.

CONFIDENTIAL

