8.2. Key Definitions

Screening Period is a Period of approximately 2-4 weeks before Day 1/Baseline during which subject eligibility is evaluated and standardized background topical therapy is introduced over a run-in Period of at least 2 weeks before Day 1/Baseline.

The Initial Period is defined as Day 1/Baseline to Week 16 (before the Week 16 dose, with last dose at Week 12). If early discontinued during treatment period, it is defined as the period until 4 weeks after last dosing date or early termination date whichever is earlier.

The Maintenance Period is defined as Week 16 (Maintenance Baseline) to Week 48. If early discontinued during treatment period, it is defined as the period until 4 weeks after last dosing date or early termination date whichever is earlier.

Follow-up Period is defined as the post end of treatment period (i.e., 1 day after end of treatment period) to Follow-up visit in respective treatment period.

The Baseline value of the Initial Period will be taken as latest valid value prior to first injection of study drug. For subjects randomized but not treated, the Baseline value will be the latest value prior to the randomization. Week 16 measurements will serve as Baseline measurements for the Maintenance Period (i.e., Maintenance Baseline). If Week 16 measurements are missing for re-randomized subjects, the last valid non-missing measurement in the Initial Period (i.e., before the dosing for Maintenance Period at Week 16 visit) will be taken as the Baseline measurement for the Maintenance Period.

For diary data (e.g., Peak Pruritus (PP) NRS, Sleep disturbance (SD) NRS), the Baseline values will be the weekly prorated average of non-missing subject diary scores reported during the 7 days. A minimum of 4 daily scores out of the 7 days is required to calculate the weekly prorated average score. Refer the details for the analysis visit window for diary data in Section 8.4.

The date of first treatment is defined as the date of first injection of study drug. The date of first treatment is the Baseline date.

The date of last treatment is defined as the date of last injection of study drug.

Study day is defined as the number of days from the date of first treatment and will be calculated as follows:

This document is confidential.

- If the event date \geq date of first treatment, study day = event date – date of first treatment + 1. Study Day 1 is therefore defined as the day of first treatment.

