8.4. Analysis Visit Windows

Efficacy by-visit summaries will use the analysis visit. Unscheduled and early termination visits will be windowed based on the following analysis visit window which is based on study day. If multiple measurements are taken within the same window, the one taken closest to the target study day will be used for the analysis. If there are multiple measurements with same difference from target day, the later assessment should be used for the analysis.

Table 8-1: Analysis Visit Window

Analysis Visit	Target Study Day	Visit Window for EASI, IGA, CCI
Baseline	1	<=1
Week 4	29	2 to 42
Week 8	57	43 to 70
Week 12	85	71 to 98
Week 15	106	NA
Week 16	113	99 to 126
Week 20	141	127 to 154
Week 24	169	155 to 182
Week 28	197	183 to 210
Week 32	225	211 to 238
Week 36	253	239 to 266
Week 40	281	267 to 294
Week 44	309	295 to 322

This document is confidential.

Week 48	337	>=323	CCI
---------	-----	-------	-----

CCI Visit window after Week 16 will not be applicable for PIQs.

CCI

For the diary data at post-baseline visit, only the diary data assessed within the timeframe below (+1 hour to end time in spec) will be considered for analysis. If >1 diary recorded on a day (within window), only one of them to take for analysis (i.e. latest one for evening diary, earliest one for morning diary).

- Evening assessment (PP/CCI NRS, CCI recorded from 17:00:00 to 00:59:59 CCI

Consecutive daily assessment:

For the evening assessments (PP NRS, CCI) during Initial Period, the daily data collected up to Week 16 will be classified into analysis visits considering the data during the 7 days immediately preceding the target study day of analysis visit. Similarly, for the morning assessment (CCI) during Initial Period, the 7 days data up to the target study day will be classified into analysis visit. Details of the analysis visit window are in the table below. Only the data belongs to Initial Period will be considered for classifying the analysis visit in Initial Period.

Table 8-2: Analysis Visit Window for Evening and Morning Assessments during Initial Period

Analysis Visit	Target Study Day of Analysis Visit	Visit Window for evening assessment (PP NRS, CCI)	CCI
Baseline*	1	-7 to -1	
Week 1	8	1 to 7	
Week 2	15	8 to 14	
Week 3	22	15 to 21	
Week 4	29	22 to 28	
Week 5	36	29 to 35	
Week 6	43	36 to 42	
Week 7	50	43 to 49	
Week 8	57	50 to 56	
Week 9	64	57 to 63	
Week 10	71	64 to 70	
Week 11	78	71 to 77	
Week 12	85	78 to 84	
Week 13	92	85 to 91	

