	14.2.1.2.4	Sensitivity Analysis of Proportion of Subjects with EASI-75 at Week 16 - Multiple Imputation (MI) Method – Initial Period	ITT Population
	14.2.1.2.5	Sensitivity Analysis of Proportion of Subjects with EASI-75 at Week 16 - Tipping Point Analysis – Initial Period	ITT Population
	14.2.1.2.7	Sensitivity Analysis of Proportion of Subjects with EASI-75 at Week 16 – LOCF – Initial Period	ITT Population
	14.2.1.2.8	Sensitivity Analysis of Proportion of Subjects with EASI-75 at Week 16 – OC – Initial Period	ITT Population

This document is confidential.

Header	Table Number	Name	Analysis Set
	14.2.1.2.9	Sensitivity Analysis of Proportion of Subjects with EASI-75 at Week 16 using Actual Stratifications - Missing as Non-Responder – Initial Period	ITT Population
	14.2.1.2.10	Subgroup Analysis of Proportion of Subjects with EASI-75 at Week 16 with Forest Plot – Missing as Non-Responder – Initial Period	ITT Population
	14.2.1.2.11	Analysis of Proportion of Subjects with EASI-75 by Visit - Missing as Non-Responder – Initial Period	ITT Population – Excluding Visits under Pandemic
14.2.2		Key Secondary Efficacy Parameters	
14.2.2.1		Key Secondary Efficacy Parameter PP NRS Improvement ≥ 4	
	14.2.2.1.1	Analysis of Proportion of Subjects with Weekly Average PP NRS Improvement ≥ 4 at Weeks 1, 2, 4 and 16 - Missing as Non-Responder – Initial Period	ITT Population
	14.2.2.1.2	Sensitivity Analysis of Proportion of Subjects with Weekly Average PP NRS Improvement ≥ 4 at Weeks 1, 2, 4 and 16 - Missing as Non-Responder – Initial Period	PP Population
	14.2.2.1.3	Sensitivity Analysis of Proportion of Subjects with Weekly Average PP NRS Improvement ≥ 4 at Weeks 1, 2, 4 and 16 - Multiple Imputation (MI) Method – Initial Period	ITT Population
	14.2.2.1.4	Sensitivity Analysis of Proportion of Subjects with Weekly Average PP NRS Improvement ≥ 4 at Weeks 1, 2, 4 and 16 - Tipping Point Analysis – Initial Period	ITT Population
	14.2.2.1.6	Sensitivity Analysis of Proportion of Subjects with Weekly Average PP NRS Improvement ≥ 4 at Weeks 1, 2, 4 and 16 – LOCF – Initial Period	ITT Population
	14.2.2.1.7	Sensitivity Analysis of Proportion of Subjects with Weekly Average PP NRS Improvement ≥ 4 at Weeks 1, 2, 4 and 16 – OC – Initial Period	ITT Population
	14.2.2.1.8	Sensitivity Analysis of Proportion of Subjects with Weekly Average PP NRS Improvement ≥ 4 at Weeks 1, 2, 4 and 16 using Actual Stratifications - Missing as Non-Responder – Initial Period	ITT Population

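### The Week 1 itch average counts the Day 1 evening score as post-treatment, although its 24-hour recall begins before the first injection

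*SAP*

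**What the plan says.** SAP Section 8.4 assigns initial-period evening diary scores to visits by "considering the data during the 7 days immediately preceding the target study day of analysis visit". In Table 8-2, Week 1 has target Day 8 and window Days 1 to 7. The baseline row (visit, target day, window) reads "Baseline* 1 -7 to -1". SAP Section 8.2 adds: "Study Day 1 is therefore defined as the day of first treatment". The Day 1 evening entry is therefore outside baseline and inside Week 1.

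The PP NRS item asks "how would you rate your itch at the worst moment during the previous 24 hours" (Protocol Section 9.1.3). SAP Section 8.4 accepts post-baseline evening entries "recorded from 17:00:00 to 00:59:59". Protocol Section 9 puts "Administration of study drug injections" last in the order of procedures at a visit but gives no clock time. A weekly average needs at least 4 daily scores (SAP Section 8.2).

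Under the key secondary parameters, the index in SAP Section 19 lists table 14.2.2.1.1: "Weekly Average PP NRS Improvement ≥ 4 at Weeks 1, 2, 4 and 16 - Missing as Non-Responder". SAP Section 10.3.3 also analyses PP NRS below 2 at Week 1, from the same window.

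The SAP handles the dosing boundary differently elsewhere. Table 8-1 puts Day 1 into baseline for EASI and IGA and starts post-baseline at Day 2. The Week 16 evening window is restricted to data before dosing.

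**The concern.** The first score counted as post-treatment looks back over a period that began before treatment. Because the item asks for the worst moment, one pre-dose peak is enough to set the score, however the skin felt after the injection. That score enters an average judged against a fixed 4-point improvement, so Week 1 response rates are pulled down. Where there is a real early effect, the treatment difference shrinks too.

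Rapid itch relief is one of the claims this trial can support: Protocol Section 6.2.3 reports onset in pruritus as early as Week 1 in phase 2b. The Week 1 window measures that claim. Key secondary endpoints are tested in sequence and testing stops at the first non-significant result (SAP Section 10), so the power of each test matters. No rule or sensitivity analysis in the public SAP leaves Day 1 out.

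**Working it through.** **1. The plan's window.** Target day minus 7 to target day minus 1: 8 − 7 = 1 and 8 − 1 = 7. This reproduces Days 1 to 7.

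**2. Is Week 1 really a key secondary time point?** The readable endpoint lists show only two Week 16 endpoints; the rest is redacted. SAP Table 7-3 is titled as having 9 endpoints. The key secondary headings in the table and figure indexes give PP NRS improvement of at least 4 at four weeks (1, 2, 4, 16), PP NRS below 2 at two (4, 16), sleep disturbance improvement at Week 16, and two composites at Week 16: 4 + 2 + 1 + 1 + 1 = 9. The count agrees, so Week 1 is one of the nine.

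**3. How much of the Day 1 recall is pre-dose?** Share = (24 − hours from injection to entry) / 24. Injection times are assumed, since none is given.

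| Injection | Entry 17:00 | Entry 20:00 | Entry 00:59 |
|---|---|---|---|
| 09:00 | 67% | 54% | 33% |
| 12:00 | 79% | 67% | 46% |
| 16:00 | 96% | 83% | 63% |

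The share exceeds half only when the entry comes less than 12 hours after the injection. It is above zero in every cell.

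**4. Effect on the response criterion.** With k entries, one of them Day 1 at zero change, the other k − 1 must average 4k/(k − 1).

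| Entries | Weight of Day 1 | Improvement needed on the other days |
|---|---|---|
| 7 | 1/7 = 14.3% | 28/6 = 4.67 |
| 6 | 1/6 = 16.7% | 24/5 = 4.80 |
| 5 | 1/5 = 20% | 20/4 = 5.00 |
| 4 | 1/4 = 25% | 16/3 = 5.33 |

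Example: baseline 7, Day 1 score 7, Days 2 to 7 all 2.5. Over Days 1 to 7 the mean improvement is (0 + 6 × 4.5)/7 = 27/7 = 3.86, a non-responder. Over Days 2 to 7 it is 4.5, a responder.

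At the lower end of the eligible range, a subject with baseline b and a score of 0 on all of Days 2 to 7 improves by 6b/7 on average. This reaches 4 only if b is at least 4.67. Entry requires 4.0, so some eligible subjects could not respond at Week 1 even with complete relief from Day 2.

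**5. Loss in treatment difference.** The documents give no Week 1 rate, SD or time course, so all inputs here are assumed: baseline mean 7.3, daily SD 1, mean improvement 1.5 to 2.5 on nemolizumab (SD 1.8 to 2.2) and 0.8 on placebo (SD 1.4).

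- Day 1 improvement zero: the difference falls from 7.3–23.6 points (Days 2 to 7) to 3.9–15.8 points (Days 1 to 7), a loss of 33% to 47%. An independent repeat gave 31% to 43%.
- Half the effect already present on Day 1: loss of 16% to 24%; the repeat gave 14% to 22%.
- A weaker set (improvement 1.0 to 2.5 on nemolizumab and 0.3 to 0.7 on placebo, SD 1.3 to 1.8, flat or gradual onset, Day 1 at zero) left only 17% to 58% of the Days 2 to 7 difference. Nemolizumab response under the current window was then 0.1% to 11%, so proportional losses are large on small rates.

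**6. Power**, two-sided 2.5%, inputs as in the first set, Day 1 at zero, two separate runs.

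- 500:250 (750 at 2:1): in the weakest scenario, 98–99% without Day 1 against 81–89% with it. With stronger onset, close to 100% either way.
- A PP NRS ≥ 7 population at its 250-subject minimum (167:83), if the same rates held: in the weakest scenario, 49–53% against 18–22%.

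**The case against.** The strongest defence is that this is a uniform and conservative convention. One 7-day rule serves every week, gives contiguous non-overlapping windows, applies to both arms, cannot inflate type I error, and works against the sponsor's own drug. All of that stands. It makes the rule safe for a claim of effect; it does not make Week 1 a clean post-treatment measure.

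Three stronger readings are tempting, and the documents support none of them.

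- A reader might infer that the Day 1 score is mostly pre-dose, or simply a baseline score. No injection time is given, and entries run to 00:59. After a 09:00 injection, any entry from 21:00 has at most half its recall before the dose. What stands is that the recall always begins before the injection and can retain a pre-dose peak.
- A reader might infer that a third to a half of the Week 1 difference is lost. That needs zero effect on Day 1 and full effect from Day 2, as well as assumed response rates. Phase 1 sits awkwardly with it: "Peak serum concentrations were observed 4 to 6 days after nemolizumab administration". If onset is gradual, Days 2 and 3 are attenuated as well. But attenuation on those days is the drug's true time course, whereas the Day 1 entry looks back past the dose. That is why only Day 1 is singled out.
- A reader might infer that a miss at Week 1 would block the other key secondary tests. The test order is redacted. If Week 1 comes late, few or no tests follow it.

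The objection that the change is more than one table cell is also fair, and is costed under the fix.

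**Conclusion.** The concern holds in a limited form. Table 8-2 treats as post-treatment a score whose recall spans the first injection, and this biases Week 1 PP NRS response toward no change. The shift in the criterion, from 4.00 to 4.67 points with 7 entries and to 5.33 with 4, is exact on one condition: the Day 1 score equals baseline. If Day 1 already shows improvement, the shift is smaller.

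The loss in treatment difference, roughly 15% to 45%, rests on assumed Week 1 rates and on the unknown Day 1 effect; weaker assumed effects give larger proportional losses. A material loss of power appears mainly with weak early effects or in a PP NRS ≥ 7 population near its minimum size. Type I error, the co-primary endpoints and Week 16 are unaffected, and any consequence for later tests in the sequence is unknown. This is a cheap improvement to the Week 1 estimate, not a flaw that threatens the trial's main conclusions.

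**What to change.** Before unblinding:

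- In Table 8-2, change the Week 1 evening PP NRS window from Days 1 to 7 to Days 2 to 7. Keep the 4-score minimum and leave all other weeks unchanged, so that Week 2 (Days 8 to 14) is not disturbed.
- State in SAP Sections 8.4 and 10.3.3 that Week 1 is an exception to the 7-day rule, because the Day 1 recall spans the first injection, and that the Day 1 entry is used in neither baseline nor Week 1.
- Report the Days 1 to 7 version as a sensitivity analysis.
- Section 8.4 reuses the evening window for other, partly redacted measures. State whether the exception extends to them.

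Cost: one table cell, short text in two sections and one extra output. Week 1 then rests on up to 6 entries instead of 7. A subject with exactly four entries, one of them Day 1, would fall below the minimum and count as a non-responder, so slightly more weekly averages would be lost.

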8.5. Pooling of Centers

Centers will not be pooled.

8.6. Subgroups

Descriptive summary and analysis for primary and selected key secondary endpoints will be produced for the following subgroups:

- Region (Europe, North America, Asia Pacific)
- Age groups (12-17, 18-65, and > 65)
- Sex
- Race
- Baseline IGA (3 or 4)
- Baseline PP NRS (≥ 7 and < 7)
- Previous use of any systemic therapy for AD (Yes, No)
- Previous use of any biologic therapy for AD (Yes, No)
- Previous use of any immunosuppressive or immunomodulatory drugs for AD (Yes, No)
- Previous use of Dupilumab for AD (Yes, No)
- Previous use of Cyclosporine for AD (Yes, No)
- Country

This document is confidential.

9. Demographic, Other Baseline Characteristics and Medication

Subject accounting, disposition, demographics, Baseline characteristics, previous therapies, and concomitant therapies by treatment will be summarized for the Initial Period and Maintenance Period.

9.1. Subject Disposition and Withdrawals

All subjects who provide informed consent will be accounted for in this study.

Subject accounting will summarize subjects screened, screen failed, randomized and randomized but not treated for the Initial Period for all subjects by overall and site. For the Maintenance Period subject randomized and subjects randomized but not treated will be summarized by overall and site, and all placebo-treated subjects will also be included for the summary.

Subject accounting by visit will be summarized by treatment group and overall for the Initial Period and the Maintenance Period at each visit (scheduled visits only).

Subject disposition will be summarized based on the ITT population by treatment group for the Initial Period and the Maintenance Period. Summaries will include subjects randomized, subjects randomized but not treated, subjects treated, subjects completed treatment, subjects discontinued treatment, primary reason for discontinuation of treatment (including summary of subjects who stopped treatment due to COVID-19), subjects completed the study, subjects discontinued from the study, primary reason for discontinuation from the study (including summary of subjects who discontinued due to COVID-19), subjects rolled over to long term extension (LTE), subjects completed Follow-up. Subjects who stopped treatment or discontinued study due to COVID-19 will be identified using "Other" specify field in CRF or "Comment as needed".

Subject disposition will also be summarized by site on the ITT population.

Screen failure will be summarized for all screened subjects. Number of subjects screened and failed will be presented. Number and percentage of reason for screen failure will be summarized.

Subjects in each analysis population (ITT, Safety, PK, and PP population only for Initial Period) will be summarized by treatment group on the ITT population for each period.

In addition, time (days since the first dose of study drug) to permanent discontinuation of study drug by reason for discontinuation will be displayed graphically in subjects having permanently discontinued from the study drug.

Maintenance Period summary will include all subjects either who completed the Initial Period and re-randomized to the Maintenance Period or who received Placebo in both Initial and Maintenance Period.

Randomization, study completion, drug completion, visit dates will be listed for the ITT population. Screen failure reason will also be listed. Additional listings of discontinuation reason, missed visit and missed assessment for subjects who discontinued due to COVID-19 will be presented for the ITT population. An additional listing for Covid-19 relevant comments will be presented for the ITT population.

Analysis population will be summarized and listed on the ITT population.

This document is confidential.

9.2. Demographic and Baseline Characteristics

All variables will be summarized by treatment group at Baseline and Maintenance Baseline respectively. Summary statistics for demographic and other Baseline characteristics will be presented for the ITT, SAF, PP and PK population.

Age (years), height (cm), weight (kg), and BMI (kg/m²) will be summarized using summary statistics for continuous variables. Age groups (12-17, 18-65, and > 65), sex, region (Europe, North America, Asia Pacific), country, race, ethnicity, and smoking status will be summarized using the summary statistics for categorical variables. Weight and BMI will additionally be presented for each age group. For the summary of height, weight and BMI in Maintenance Period, Maintenance Baseline will be used.

The Baseline disease characteristics, EASI, IGA, weekly average PP-NRS, PP-NRS (<7 and ≥7), weekly average AP-NRS, weekly SD-NRS, CCI will be summarized. IGA will be summarized as a categorical variable. For Maintenance Period, Maintenance Baseline will be used to summarize.

A summary table for the stratification factors will be provided to show any discrepancies between what was reported through Interactive Voice Response System (IVRS)/Interactive Web Response System (IWRS) versus stratification using actual data at Baseline. Actual PP-NRS score will be derived using the diary data.

All demographic and baseline characteristics data will be listed on the ITT population.

